## 2. Objectives

### CIP chapter 7.1 Objectives

*This study is designed as a post-market clinical follow-up study to identify and evaluate residual risks associated with the use of the BIOMONITOR III system that are discovered or remain even after risk analysis, risk mitigation and successful conformity assessment. The results will be used to update the clinical evaluation. Furthermore, the study will also provide additional data as required by regulatory authorities outside of the CE-region.*

## 3. Investigational Device

### CIP chapter 4 Investigational device

*The devices used in this clinical investigation are the following BIOTRONIK devices:*

- BIOMONITOR III incl. Incision Tool and Insertion Tool (FIT OneStep)
- Programmer devices ICS 3000 or Renamic
- Programmer Software PSW 1901.A/S
- CardioMessenger (different models)
- Remote Assistant III

## 4. Study Design & Time Course

### CIP chapter 8.1 General considerations

*The BIO|MASTER.BIOMONITOR III is designed as an open, prospective, single arm, non-randomized international study.*

### CIP chapter 8.1.4 Methods

*During the course of the study, all clinical procedures are performed according to clinical routine. All parameters and measurements that are recorded within the study are described in this section and are documented on the following electronic Case Report Forms (eCRFs). The corresponding time schedule is described in section 9.1:*

- Enrollment
- Baseline
- Medical History
- Insertion
- 1st follow-up
- 3-month follow-up
- 12-month follow-up
- Adverse Event
- Device Deficiency

- *Device Log*
- *Explantation/Deactivation*
- *Concomitant Medication Log*
- *Deviation Log (site)*
- *Device Accountability Details (for Australia only)*
- *Termination*

## 5. General Statistical Procedures

### 5.1. Descriptive analyses

CIP chapter ...

...

For continuous variables descriptive statistics (mean, standard deviation, minimum, 1. quartile, median, 3. quartile and maximum) will be calculated. For nominal variables absolute numbers and relative frequencies based on the non-missing data will be determined. Ordinal data are described by the 1st quartile, median, and 3rd quartile as well as the absolute numbers and relative frequencies based on the non-missing data of each category.

For illustration, see the following standard tables with and without subgroup analyses based on dummy data.

#### Nominal – dichotomous data

| Variable
(N total = 10) | Category | N non-missing             | Absolute frequency | Relative frequency [%] |
|----------------------------|----------|---------------------------|--------------------|------------------------|
| Sex                        | Female   | 9                         | 5                  | 55.6                   |
| History of AF              | Yes      | 8                         | 4                  | 50.0                   |
| Variable
(N total = 10) | Category | Group Randomization group | N non-missing      | Absolute frequency     |
| Sex                        | Female   | Control (N group = 3)     | 3                  | 2                      |
|                            |          | Therapy 1 (N group = 4)   | 4                  | 3                      |
|                            |          | All                       | 9                  | 5                      |
| History of AF              | Yes      | Control                   | 2                  | 0                      |
|                            |          | Therapy 1                 | 4                  | 3                      |
|                            |          | All                       | 8                  | 4                      |

#### Nominal data – more than two categories

| Variable
(N total = 10)            | N non-missing             | Very good N(%) | Good N(%)      | Medium N(%) | Poor N(%)   |
|---------------------------------------|---------------------------|----------------|----------------|-------------|-------------|
| Patient self assessment at enrollment | 7                         | 2 (28.6%)      | 2 (28.6%)      | 1 (14.3%)   | 2 (28.6%)   |
| Patient self assessment at 12m FU     | 8                         | 1 (12.5%)      | 3 (37.5%)      | 3 (37.5%)   | 1 (12.5%)   |
| Variable
(N total = 10)            | Group Randomization group | N non-missing  | Very good N(%) | Good N(%)   | Medium N(%) |
| Patient self assessment at enrollment | Control (N group = 3)     | 2              | 1 (50.0%)      | 0 (0.0%)    | 0 (0.0%)    |
|                                       | Therapy 1 (N group = 4)   | 3              | 0 (0.0%)       | 1 (33.3%)   | 1 (33.3%)   |
|                                       | All                       | 7              | 2 (28.6%)      | 2 (28.6%)   | 1 (14.3%)   |
| Patient self assessment at 12m FU     | Control                   | 2              | 0 (0.0%)       | 1 (50.0%)   | 0 (0.0%)    |
|                                       | Therapy 1                 | 4              | 0 (0.0%)       | 2 (50.0%)   | 1 (25.0%)   |
|                                       | All                       | 8              | 1 (12.5%)      | 3 (37.5%)   | 1 (12.5%)   |

Scale / metric data

| Variable
(N total = 10)            |                                 | N non-missing | Mean  | SD   | Min   | Lower quartile | Median | Upper quartile | Max   |
|---------------------------------------|---------------------------------|---------------|-------|------|-------|----------------|--------|----------------|-------|
| Age [years]                           |                                 | 7             | 51.7  | 15.0 | 25.0  | 40.0           | 57.0   | 60.0           | 70.0  |
| Height [cm] as measured at enrollment |                                 | 8             | 177.3 | 14.4 | 150.0 | 170.0          | 179.0  | 187.5          | 195.0 |
| Variable
(N total = 10)            | Group
Randomization
group | N non-missing | Mean  | SD   | Min   | Lower quartile | Median | Upper quartile | Max   |
| Age [years]                           | Control
(N group = 3)        | 2             | 55.0  | 7.1  | 50.0  | 50.0           | 55.0   | 60.0           | 60.0  |
|                                       | Therapy 1
(N group = 4)      | 3             | 56.7  | 15.3 | 40.0  | 40.0           | 60.0   | 70.0           | 70.0  |
|                                       | All                             | 7             | 51.7  | 15.0 | 25.0  | 40.0           | 57.0   | 60.0           | 70.0  |
| Height [cm] as measured at enrollment | Control                         | 3             | 183.3 | 10.4 | 175.0 | 175.0          | 180.0  | 195.0          | 195.0 |
|                                       | Therapy 1                       | 3             | 175.0 | 21.8 | 150.0 | 150.0          | 185.0  | 190.0          | 190.0 |
|                                       | All                             | 8             | 177.3 | 14.4 | 150.0 | 170.0          | 179.0  | 187.5          | 195.0 |

Ordinal data

| Variable
(N total = 10) |                                 | N
missing  | Min | Lower
quartile | Median | Upper
quartile | Max |
|----------------------------|---------------------------------|---------------|-----|-------------------|--------|-------------------|-----|
| NYHA class enrollment      |                                 | 2             | 1.0 | 1.0               | 1.0    | 2.5               | 4.0 |
| NYHA class 24m             |                                 | 3             | 1.0 | 1.0               | 1.0    | 3.0               | 4.0 |
| Variable
(N total = 10) | Group
Randomization
group | N non-missing | Min | Lower quartile    | Median | Upper quartile    | Max |
| NYHA class enrollment      | Control
(N group = 3)        | 3             | 1.0 | 1.0               | 1.0    | 3.0               | 3.0 |
|                            | Therapy 1
(N group = 4)      | 4             | 1.0 | 1.0               | 1.5    | 3.0               | 4.0 |
|                            | All                             | 8             | 1.0 | 1.0               | 1.0    | 2.5               | 4.0 |
| NYHA class 24m             | Control                         | 2             | 1.0 | 1.0               | 2.0    | 3.0               | 3.0 |
|                            | Therapy 1                       | 3             | 1.0 | 1.0               | 2.0    | 4.0               | 4.0 |
|                            | All                             | 7             | 1.0 | 1.0               | 1.0    | 3.0               | 4.0 |

## 5.2. Inferential analyses

For the primary endpoint, a one-sample one-tailed binomial test will be carried out. Furthermore, a 95% confidence interval (Wilson-score method) for the SADE-free rate will be calculated. Hence, a Kaplan-Meier curve will be plotted.

Since all secondary endpoints are hypothesis-free, no inferential statistics will be carried out. Nonetheless, 95% confidence intervals for the respective parameters will be calculated.

## 5.3. Significance level

*CIP chapter 11.3: Level of significance and the power of the study*

*The significance level alpha is 0.025, the power is set to 90%.*

A one-sided p-value  $< 0.025$  is considered to indicate statistical significance. No adjustment for multiple testing is foreseen, i.e. all analyses except those related to the primary endpoint are considered to be exploratory.

## 5.4. Missing Data

*CIP chapter 11.11 Handling of missing, unused and spurious data*

*Missing or spurious data will not be imputed and not be used for analysis. More details will be specified in the SAP.*

Missing data will not be imputed. Free text will be used to clarify other data. Spurious data will be clarified via the query management, i.e. corrected after approval of an investigator. Remaining outliers will be identified during the review of the data before data base closure and will be reported in the Blind Review Report. In case of a clear evidence of a measurement error, the Statistical Analysis Plan will be updated in order to avoid any bias. Spurious data, which were not clarified by the query process before database closure, will be indicated. If appropriate, analyses will be performed both with /without such data.

## 5.5. Exclusion of data from confirmatory data analysis

*CIP chapter 11.12 Exclusion of data from the confirmatory data analysis*

*In the following cases, data are to be excluded from analysis of the primary endpoint:*

- *No data are allowed to be collected and included in the absence of a documented consent.*
- *Data of patients will be excluded from analysis in case a patient terminates the study prior to any insertion attempt.*

- Patients without primary endpoint but premature study termination earlier than 77 days after insertion (91 days = 3 month minus 14 days tolerance) are not included in the analysis set to avoid an over-estimation of the SADE-free rate.
- Any event that occurred later than the pre-specified time window for the 3-month follow-up in patients who did not have a 3-month follow-up (91 days plus 14 days tolerance = 105 days) does not contribute to the primary endpoint.
- SADEs will be adjudicated by an internal adjudication board, whereby the investigator assessment of seriousness and device relatedness will be re-examined.

The analysis will use all data that are stored in the study database. It is in the responsibility of the persons entering data and of those checking data before the final data export that the data comply with the approval of the patient.

## 5.6. Subgroups

### CIP chapter 11.9 Specification of subgroups

No subgroups are defined.

## 5.7. Interim analyses

### CIP chapter 11.6: Provisions for an interim analysis

The main differences between BioMonitor 2 and BIOMONITOR III are limited to a reduced device size and a novel simplified injection-like insertion procedure. The focus of this study is primarily on the safety of the BIOMONITOR III system including the insertion procedure.

Therefore the primary endpoint is to evaluate the SADE-free rate related to the BIOMONITOR III and the incision and insertion tool set from insertion until the 3-month follow-up. When all enrolled patients have either completed the 3-month follow-up or their study participation has been terminated, the data for the primary endpoint are completed. At this point in time, an interim Clinical Investigation Report will be written. The content of this report will be pre-defined in a Statistical Analysis Plan.

Individual data collected in this study, which do not concern the primary endpoint, may be analysed before the study is completed. If they shall be published, the stipulations of section 21 apply. Safety reasons, the support of regulatory submissions and publication opportunities may trigger unscheduled interim analyses.

Such unplanned interim analyses and reports, if any, will contain at least descriptive statistics of baseline and insertion data and descriptive statistics of the defined endpoints. Inferential statistics of endpoints may be included to support publication activities. The precise scope of each interim analysis will be defined in the SAP before the individual interim analyses.

In case of a suspension of the clinical investigation, an interim analysis will be performed to generate a clinical investigation report according to the MDR requirements. No multiplicity adjustment is foreseen.

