11.5 Pass/fail criteria

The clinical investigation is deemed to be passed, if the primary hypothesis H_0 is rejected.

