11.6 Provision for an interim analysis

The main differences between BioMonitor 2 and BIOMONITOR III are limited to a reduced device size and a novel simplified injection-like insertion procedure. The focus of this study is primarily on the safety of the BIOMONITOR III system including the insertion procedure.

Therefore the primary endpoint is to evaluate the SADE-free rate related to the BIOMONITOR III and the incision and insertion tool set from insertion until the 3-month follow-up. When all enrolled patients have either completed the 3-month follow-up or their study participation has been terminated, the data for the primary endpoint are completed. At this point in time, an interim Clinical Investigation Report will be written. The content of this report will be pre-defined in a Statistical Analysis Plan.

Individual data collected in this study, which do not concern the primary endpoint, may be analysed before the study is completed. If they shall be published, the stipulations of section 21 apply. Safety reasons, the support of regulatory submissions and publication opportunities may trigger unscheduled interim analyses.

Such unplanned interim analyses and reports, if any, will contain at least descriptive statistics of baseline and insertion data and descriptive statistics of the defined endpoints. Inferential

statistics of endpoints may be included to support publication activities. The precise scope of each interim analysis will be defined in the SAP before the individual interim analyses.

In case of a suspension of the clinical investigation, an interim analysis will be performed to generate a clinical investigation report according to the MDR requirements. No multiplicity adjustment is foreseen.

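### Do unscheduled, unadjusted interim reports put the 2.5% error level of the primary safety test at risk?

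*SAP*

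**What the plan says.** Protocol 11.6 and SAP 5.7 carry the same text. They fix one report on the primary endpoint, at the point when every patient has had the 3-month visit or has left the study. At that point "the data for the primary endpoint are completed".

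The next paragraph turns to earlier analyses: "Individual data collected in this study, which do not concern the primary endpoint, may be analysed before the study is completed". It then names safety, regulatory submissions and publication as possible triggers for unscheduled analyses, with no limit on number or timing. Such a report "will contain at least descriptive statistics of baseline and insertion data and descriptive statistics of the defined endpoints", and "Inferential statistics of endpoints may be included to support publication activities". One control follows: "The precise scope of each interim analysis will be defined in the SAP before the individual interim analyses". If the study is suspended, "an interim analysis will be performed to generate a clinical investigation report according to the MDR requirements". The section closes: "No multiplicity adjustment is foreseen".

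Four other places bear on the point:

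- Protocol 11.5: "The clinical investigation is deemed to be passed, if the primary hypothesis H_0 is rejected".
- Protocol 11.7 sets no termination criteria on statistical grounds.
- SAP 5.2 gives a test to the primary endpoint only. The secondary endpoints get confidence intervals.
- SAP 5.3 sets one-sided 0.025, foresees no adjustment, and calls everything exploratory except analyses of the primary endpoint.

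**The concern.** Read together, these sections seem to leave a door open. An unscheduled report may contain inferential results on endpoints. The only endpoint with a specified test is the primary one, and SAP 5.3 does not label a primary-endpoint analysis exploratory. Protocol 11.5 asks only that the null hypothesis be rejected, without saying in which analysis. If a rejection in an early report could count as a pass, the study would have several chances to succeed, each at an unadjusted 2.5%.

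At stake would be the error level of the one confirmatory claim, that the SADE-free rate exceeds 90%. An early p-value could also reach a submission or a paper with its status unclear.

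**Working it through.** **Inputs from the documents.** Null SADE-free rate 90% and exact binomial test (SAP 10.4); one-sided alpha 0.025 (SAP 5.3); expected rate 97%, power 90%, drop-out 10% (Protocol 11.2); enrollment of about 9 months (Protocol 8.3.7).

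**The plan's own sample size.** The normal approximation gives

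n = [(1.960·√(0.90·0.10) + 1.282·√(0.97·0.03)) / 0.07]² = 132.8, so 133.

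The exact calculation gives 141 as the first n from which power stays above 90%. Then 141/0.9 = 156.7, so 157. All of these agree with Protocol 11.2.

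**The planned test.** Let X be the number of patients with a SADE, binomial with probability 0.10 under the null.

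- n = 141: reject if X ≤ 7. Error P(X ≤ 7) = 0.0242; power at 97% is 93.7%.
- n = 157: reject if X ≤ 8. Error P(X ≤ 8) = 0.0207; power 95.2%.

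The single test holds its level. Reports written after the 3-month data are complete cannot change it, because the primary data no longer move.

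**If one early rejection could count as a pass.** The plan does not provide for this; the calculation shows what it would cost. With fewer than 36 patients no rejection is possible, since 0.9³⁵ = 0.0250 (just above 0.025) and 0.9³⁶ = 0.0225. Above that, the answer depends on who is counted at the look. My assumptions, not in the documents, are entry uniform over 273 days, one look at day 182, 227 or 273, no drop-out, and SADE onset uniform over the first 14 or the first 91 days.

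| Patients counted at the early look | Final n = 141 | Final n = 157 |
|---|---|---|
| Protocol 7.2.1 formula: 3-month visit reached, or event | 2.4% to 2.5% | 2.0% to 2.2% |
| Only patients with 91 days of follow-up | 3.1% to 3.3% | 2.9% to 3.0% |

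The first row barely moves because, at an early cut, the Protocol 7.2.1 formula counts events in patients still in follow-up but leaves out their event-free peers. It therefore leans against the device. For n = 141 at day 273, the chance of an early rejection is only 0.0006 (14-day onset) or 0.0027 (91-day onset).

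The second row comes from averaging an exact two-look calculation over the number of patients who have reached day 91. At day 182 that number averages 141·(182−91)/273 = 47, and the total error is 0.0317. At days 227 and 273 it is 0.0330 and 0.0314.

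For comparison, one extra look at a fixed, fully evaluable cohort gives between 0.0242 and 0.0430 for final n = 141. A look at 70 patients gives 0.0408, and the maximum is at 36.

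**Which analysis Protocol 11.5 means.** It refers to the primary hypothesis. Protocol 7.2.1 states that hypothesis for a rate defined at the 3-month visit. Section 11.6 says when the data for it are complete and attaches a report. SAP 5.2 and 10.4 specify one test of it. The deciding analysis is implied, though not named.

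**The case for a change.** The best case for a change is that each safeguard is partial.

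- The sentence on data unrelated to the primary endpoint permits; it does not forbid. The next paragraph then requires unscheduled reports to describe the defined endpoints, which include the primary one.
- The duty to define each interim in the SAP first governs scope, not confirmatory status. Protocol 11.8 lets the SAP be updated until database closure. The study is open and single-arm, with no data monitoring committee (Protocol 18.11), so scope could be written with SADE counts in view.
- SAP 10.1 includes patients who missed the 3-month visit but had not terminated before day 77. Applied literally at an early cut, that sentence would count patients not yet followed as successes. One look would then give 2.6% to 3.5% with 14-day onset and about 8% to 10% with 91-day onset.
- Several looks would cost more than one. Fixed-cohort looks at 60, 80, 100 and 120 before a final 141 give 4.6%.

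The first two points stand as descriptions of the text. Neither creates a route to success: a p-value in an unscheduled report is not a pass decision, follow-up goes on, and the planned test is still run. Under a suspension too, Protocol 20.3 continues follow-up and data collection.

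The third point does not stand. The SAP 10.1 sentence concerns patients who did not attend a visit that was due, and it was written for complete data. Its larger figures also need onset spread evenly over three months, whereas Protocol 5.3 expects most complications early. The fourth needs both a series of looks and a rule that any of them may decide, and the plan has neither.

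**Conclusion.** The concern does not call for a change. Followed as written, the plan has one confirmatory test on complete 3-month data, with error 2.4% (141 evaluable) or 2.1% (157), both within 2.5%. Inflation needs a rule that an early rejection counts as a pass, and the documents contain none. Under the Protocol 7.2.1 denominator one early look would add nothing material even then; restricted to patients with full 3-month follow-up it would bring the error to about 3%. Both results rest on the assumed entry pattern, look dates and absence of drop-out, and the first also on the assumed onset times.

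What remains is missing detail: the status of an optional early p-value is not stated. The analyst who writes the scope of an unscheduled report into the SAP would naturally mark any primary-endpoint result before the 3-month data are complete as descriptive or exploratory. A sentence saying so would be harmless, but the planned test, its level and the sample size do not depend on it.

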## **5.8. Software**

All analyses will be carried out using validated software, e.g. SAS version 9.4 or upgrades.

## 6. Specific Study Dates

### 6.1. Enrollment date

| Data file, identifier
patient_display_id_full | Variable
name | Variable
label             | Variable
level | Nominal
values |
|--|------------------|-------------------------------|-------------------|-------------------|
| enrollment                                       | DMICDT           | Patient: Date of IC signature | date              | n.a.              |

### 6.2. Insertion date

| Data file, identifier
patient_display_id_full | Variable
name | Variable
label           | Variable
level | Nominal
values |
|--|------------------|-----------------------------|-------------------|-------------------|
| insertion  | PRIMSTDT         | Date of insertion procedure | date              | n.a.              |

